9.2.2 Secondary End Points

Secondary endpoints (sEP) are:

- 1) the best corrected visual acuity (BCVA) in BCVA letter scores (EDTRS charts) per visit;
- 2) central subfield thickness (CST) measured by OCT per visit;
- 3) the number of Ranibizumab injections required (after three initial monthly injections) according to re-treatment criteria (see 6.3) until “success” is reached as well as up to month 29 after randomisation (the entire period of observation, in case of late recurrence of ME);

All these items are measured at every mandatory visits, at latest at Month 29.

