5.3.4 Alternative Medication

Patients may not receive any treatment (approved or investigational) for their CRVO in the study eye other than the study treatment with Ranibizumab. Patients without response to Ranibizumab will be switched to an alternative intravitreal drug (Aflibercept or Dexamethasone implant), which will be given out of the study (see chapter 6.5).

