6.3 Description of the Treatment Procedures

Intravitreal injections of Ranibizumab will be applied in all patients according to treatment guidelines. The experimental group will receive an additional targeted laser photocoagulation of the peripheral areas of capillary non-perfusion (up to 4 laser treatments within 1st year of the study). No further additional treatments of the study eye will be given in any of the arms of the trial.

Intervention scheme of CoRaLa II Trial

* complementary endpoints in all patients at month 24.

** secondary endpoints in patients with success at that visit when success is stated; in patients without treatment success prior to visit 24, secondary endpoints will be assessed at month 29; if a patient needs treatment after success, this treatment is no longer a study treatment and therefore no further AE/SAE documentation is needed.

Based on the results of optical coherence tomography (OCT) the **diagnosis of ME** will be established and Ranibizumab injections will be indicated.

Pre-defined re-treatment criteria will be applied according to treatment guidelines in order to identify a further need of re-injections at the monthly visits.

Re-treatment with Ranibizumab is needed if the following criteria are met:

- persisting ME or
- recurrence of ME

defined as presence of intra-/sub-retinal fluid and /or central subfield thickness (**CST**) of **≥250 µm** assessed by OCT

Re-treatment criteria for laser photocoagulation: new areas of capillary non-perfusion detected with fundus photography and FA at 3 and 9 months after randomisation. Experienced graders of the CoRaLa II Central Reading Center will evaluate all fundus and FA images taken with the Zeiss 700 device and define the non-perfused retinal areas for laser photocoagulation. Laser photocoagulation will be performed at Month 2 and if needed at Months 4, 6 and 10.

Parameters needed for end-point evaluations:

- Only if no ME can be identified by OCT over 6 months of follow-up **treatment success** is stated and the time until this visit will be used in confirmatory analysis.

- **The number of Ranibizumab injections** depends on the valid assessment of presence/ or absence of ME in all monthly visits and will be counted until defined success (if applicable) and at the end of study.

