Safety visit and end of (S)AE report period (4 weeks after EoT) for patients who still need monthly intravitreal injections (no success reached).

- Blood pressure and pulse
- QoL (Visual Function Questionnaire) before the ophthalmologic investigation will be performed
- Documentation of Adverse events, critical ocular events and Concomitant medication
- Ocular assessment (assess prior to injection, assess in the study eye only, see exceptions in text below):
 - Investigation of BCVA using ETDRS chart **performed by a blinded assessor in both eyes!**
 - IOP
 - Gonioscopy
 - Slit lamp biomicroscopy
 - Visual field performed **in both eyes!**
 - OCT **in both eyes!** (in addition OCT will be evaluated by the CoRaLa II Central Reading Center)
 - OCT-Angiography **in both eyes!** (in addition OCT-Angiography will be evaluated by the CoRaLa II Central Reading Center)
 - Ophthalmoscopy performed **in both eyes!**

- Fundus photography and Fluorescein angiography (FAG) **in both eyes!** performed according to the imaging protocol and evaluated by the CoRaLa II Central Reading Center.
- Documentation if an injection with Ranibizumab was needed. (Injections of Ranibizumab after Months 23 are no longer documented as study treatment.)

6.4 Follow-up Visit 25 (month 29 +/- 7 days) **EoS** is a mandatory visit for all patients

Ocular assessment (study eye only) providing the final assessment of all secondary endpoints and any potentially late occurrence of critical ocular events.

- Blood pressure and pulse
- Critical ocular events and Concomitant medication
- Ocular assessments in study eye only:
 - Investigation of BCVA using ETDRS chart **performed by a blinded assessor**
 - IOP
 - Slit lamp biomicroscopy
 - OCT (in addition OCT will be evaluated by the CoRaLa II Central Reading Center)
 - OCT-Angiography (in addition OCT-angiography will be evaluated by the CoRaLa II Central Reading Center)
 - Ophthalmoscopy
- Documentation how many injections with Ranibizumab were needed. (Injections of Ranibizumab after Months 23 are no longer documented as study treatment.)

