6.5.2 Rescue Treatment

Patients with progress of neovascular complication (Increase of NVE's or NVD's, neovascular glaucoma) will receive rescue treatment with pan-retinal photocoagulation (PRP) outside the study intervention.

Patients with persisting macular edema without response to Ranibizumab will be treated with intravitreal Aflibercept (Eylea) or dexamethasone implant (Ozurdex) out of the study.

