6.6 Plan for Further Treatment

In case the patients will suffer from a recurrence of macular edema with impaired BCVA after month 23 (End of treatment visit) of the study, further treatment with anti-VEGF drugs (Ranibizumab or Aflibercept) or other treatment methods (e.g. application of Dexamethasone implant = Ozurdex) will be offered depending on investigators decision.

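### The month 29 injection count (9.2.2 item 3) records ranibizumab only, so an eye whose macular edema is by then treated with aflibercept or dexamethasone adds nothing to it

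*Protocol*

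**What the plan says.** Section 9.2.2 item 3 defines the endpoint as "the number of Ranibizumab injections required (after three initial monthly injections) according to re-treatment criteria (see 6.3"), until success and "as well as up to month 29 after randomisation (the entire period of observation, in case of late recurrence of ME"). The 6.3 criteria rest on OCT alone: intra- or subretinal fluid, or a central subfield thickness of at least 250 µm.

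Three other sections govern edema that persists or returns:

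- Section 5.3.4: "Patients without response to Ranibizumab will be switched to an alternative intravitreal drug", namely aflibercept or a dexamethasone implant.
- Section 6.5.2: "Patients with persisting macular edema without response to Ranibizumab will be treated with intravitreal Aflibercept (Eylea) or dexamethasone implant (Ozurdex) out of the study".
- Section 6.6: for "a recurrence of macular edema with impaired BCVA after month 23", patients are offered "further treatment with anti-VEGF drugs (Ranibizumab or Aflibercept) or other treatment methods", and the investigator decides.

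The last in-trial injection is at month 23 (1.2.1). Visit 24 (6.3.5) records whether a ranibizumab injection was needed. Visit 25 at month 29 (6.4) asks for "Documentation how many injections with Ranibizumab were needed". Neither visit's list includes an assessment of the re-treatment criteria. Both record concomitant medication. Patients who end therapy early are still offered the month 29 visit, unless they withdrew consent (6.5.1).

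**The concern.** The count is extended to month 29 in order to pick up late recurrence. It fails to do so when the recurrence is treated with another drug that the protocol itself permits. An eye that responds poorly to ranibizumab and moves to aflibercept stops contributing, and its total looks like that of an eye that needed no more treatment.

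This matters because the injection count has its own sample-size calculation in 9.4, and because the benefit argued in 1.1 is fewer re-injections for recurrent edema, whatever the drug. Switching is a known possibility: section 1.1 reports that after the proof-of-concept study single patients with recurrence were moved to aflibercept or dexamethasone. What is at stake is the estimated difference in treatment burden.

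**Working it through.** **1. The plan's own figure.** Section 9.4 gives 5.6 (SD 4.9) injections for R-only and 2.8 (SD 2.7) for RL within two years, without the three loading injections. It asks for 46 per group at two-sided 5% and 90% power. The difference is 2.8 and the root-mean-square SD is √((4.9² + 2.7²)/2) = 3.96. An unequal-variance t-test needs 44 per group (power 0.905) and has power 0.917 at 46. Allowing for the Wilcoxon efficiency, 44/0.955 ≈ 46. The stated figure stands.

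**2. What is counted, set against what is given.**

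| Situation | Treatment allowed | In the 9.2.2 count? |
|---|---|---|
| Edema meeting 6.3, to month 23 | Ranibizumab | Yes |
| No response to ranibizumab (5.3.4, 6.5.2) | Aflibercept or dexamethasone implant, out of study | No |
| Recurrence with impaired acuity after month 23 (6.6) | Ranibizumab | Asked about at visits 24 and 25, but not given under 6.3 |
| Same | Aflibercept or another method | No |

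**3. Size to month 23.** The protocol gives no switch rate, so the rate is assumed and set equal in both arms. Counts are modelled as negative binomial, matched to the 9.4 means and SDs, with size = mean²/(SD² − mean):

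- R-only: 5.6²/(4.9² − 5.6) = 1.70
- RL: 2.8²/(2.7² − 2.8) = 1.75

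Values above 20 are set to 20, the maximum in 3.1. The capped means are 5.53 and 2.80, a difference of 2.73. More than 6 maintenance injections are needed by 33% of R-only and 10% of RL eyes. Each eye whose count would exceed c is held at c with probability p:

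| c | p = 10% | p = 25% | p = 50% |
|---|---|---|---|
| 6 | 5% lost | 12% lost | 25% lost |
| 9 | 3% lost | 7% lost | 13% lost |
| 12 | 1% lost | 3% lost | 7% lost |

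For c = 6 the R-only mean falls by 0.16, 0.41 or 0.82 and the RL mean by 0.03, 0.07 or 0.14. The difference becomes 2.60, 2.39 or 2.05. Unequal-variance t-test power at 55 per arm is 0.956, 0.946 or 0.928, against 0.962 without switching.

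**4. Size in months 24 to 29.** Read the 9.4 planning rates as 50% of R-only and 20% of RL eyes still under treatment at two years. Assume 3 treatments each in this period. The true difference then grows by (0.50 − 0.20) × 3 = 0.9, from 2.8 to 3.7. If a share s of those treatments uses another drug, the count loses 0.9 × s:

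- s = 10%: 0.09 (2.4% of 3.7)
- s = 25%: 0.225 (6.1%)
- s = 50%: 0.45 (12.2%)

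Range for the assumed 3 treatments:

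- With 1.8 each (half of the 3.6 injections in the third year that 1.1 cites), the loss is 0.05 to 0.27 of 3.34, or 1.6% to 8.1%.
- With 6 each (monthly), it is 0.18 to 0.90 of 4.6, or 3.9% to 19.6%.

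**The case against.** The trial asks about the need for ranibizumab, so a ranibizumab count is a legitimate endpoint. Late recurrence has another route: 9.5.1 promises separate reporting of relapses after success, and 1.2.1 has the month 29 visit document relapses treated out of the trial. Concomitant medication is recorded, so other drugs may be recoverable, and an analysis plan that is not shown could add a rule for switched eyes. All of that stands, and it is why the ranibizumab count should stay. It does not change what the protocol fixes as item 3, which excludes other drugs in the very period added to capture recurrence.

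A reader might infer more than the documents support:

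- **That out-of-study ranibizumab is also lost.** Section 6.3 does say "if a patient needs treatment after success, this treatment is no longer a study treatment", but that sentence goes on to draw a consequence for adverse event documentation only. The same section counts injections at the end of study, and visits 24 and 25 ask about ranibizumab after month 23.
- **That the bias must work against the laser arm.** That follows from a switch triggered by a high count. The protocol's trigger is lack of response. An eye that dries after each injection and then recurs has a high count but responds, while a true non-responder may switch early in either arm.
- **That the stopping point varies by site**, because 6.5.1 says termination may be considered where 5.3.4 and 6.5.2 say the switch will happen. The 6.5.1 wording introduces a general list of reasons, so site variation is conjecture.
- **That the comparison loses its power.** This needs heavy, one-sided switching. If 20% of R-only eyes and no RL eyes each had 8 uncounted treatments, the difference would be 2.8 − 0.20 × 8 = 1.2. The only evidence in the protocol is of single cases.

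**Conclusion.** The point holds as a limited defect in the definition. As written, the month 29 count is not the total need that its stated purpose implies: it omits every treatment of macular edema with another drug, and its late ranibizumab part is not given under 6.3. It therefore understates treatment need in any eye that switches.

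The effect on the between-arm difference depends on assumptions. If switching follows high counts equally in both arms, about 1% to 25% of the difference to month 23 is lost, plus 0.09 to 0.45 injections in months 24 to 29 (about 2% to 12% of 3.7, at 3 treatments each). If switching removed more treatments from RL than from R-only, the difference would be overstated instead. Under the equal-switching model to month 23, power at 55 per arm stays at 93% to 96%, so significance is little affected. The months 24 to 29 part lies outside the two-year comparison sized in 9.4. Nothing here bears on the primary endpoint. Severity is low to moderate; this is a cheap improvement.

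**What to change.** 1. In 9.2.2 item 3 (with 2.2 and the synopsis), keep the ranibizumab count and label it as ranibizumab under the 6.3 criteria while on study treatment, to month 23 at the latest.
2. For the whole period to month 29, add a count of all intravitreal treatments for macular edema in the study eye, in or out of the study. Report it in total and by drug, and compare it between arms.
3. In 6.3.5 and 6.4, replace the ranibizumab question with one on intravitreal treatments for macular edema since the last visit, by drug and date. Ask it also of patients who ended therapy early and attend month 29 (6.5.1).

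Cost: one changed eCRF item at visits 24 and 25 and a protocol amendment, which may need ethics committee and authority approval under 10.3 and comes after recruitment began. No visits, patients or imaging are added. The all-drug total mixes injections with implants, which need not be exchangeable, hence the report by drug. Treatment intervals outside the study also remain uncontrolled.

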9.2.3 Further complementary outcomes including quality of life

- proportion of subjects developing neovascularization(s) of retina, optic disc, and/or in anterior segment over the total period of observation.
- patient-reported health-related quality of life (QoL) will be investigated at BL and at the end of study. It is measured by the Visual Function Questionnaire VFQ25 [28], which focuses on functional aspects in case of impaired visual acuity. It has been proven to have satisfying properties regarding validity, reliability and sensitivity to change in English and German. Patients will complete the questionnaire before the ophthalmologic investigation will be performed at the baseline and at month 12 and 24. We expect most patients to understand the questions in the questionnaire.

Because QoL is a complementary endpoint only we refrain from having an exclusion criterion on language. The pre-post change in the QoL will be analysed.

- vessel density (assessed by OCT-angiography, see also sec. 7) will be quantified by a metric measure with the range [0;1].
- area of the foveal avascular zone (FAZ, assessed by OCT-angiography, see also sec. 7, in [mm²])
- the area of non-perfusion (assessed by FA) will be quantified as sum of all areas identified (see also sec. 7);
- a potential visual field loss will be quantified as follows: for each patient the retinal sensitivities over all points tested will be summed-up and divided by the number of points investigated. The harmonized mean per group will be calculated per group and visit. The change between the two timepoints (Months 4 and 24) per arm will be used to characterize the both groups and be compared between treatment arms (see also sec. 7);
- the number of visits with applied laser treatment and the laser spots applied in the experimental group (RL-arm) will be counted for descriptive reasons and be compared between treatment arms.

9.2.4 Safety characteristics

(Serious) adverse reactions (S)ARs and critical ocular events will be compared between the

arms to describe the safety profiles of the combined intervention.

9.3 Statistical Description of the trial hypothesis

9.3.1 Statistical Hypotheses/Statistical Estimation Method

It is to be assessed whether there is a difference in the times to reach treatment success as defined in the primary. The statistical hypotheses are:

- H_0 : Time to success (experimental group) = Time to success (control group)
- HA : Time to success (experimental group) \neq Time to success (control group)

9.4 Sample Size Discussion

Long-term review of CoRaLa I [10] patients (as reported in 1.2) showed that a proportion of $p_{R\text{-only}}=0.58$ had to be treated longer than 2 years, while for all but one patient ($p_{RL}=0.1$) the combined therapy could be terminated after median [quartiles] of 10 [3;11] months but total observation times of 18 [16; 20] months.

Assuming 2 years to treatment success, rates of 50% with R-only and (conservative) 20% with RL, setting a two-sided significance level α at 5%, and requiring 90% power we need a total of $N=92$ cases with a log rank test.

With regard to the number of injections applied within two years (without the three initial monthly injections), we observed 5.6 (4.9) injections (mean (SD)) in the R-only, but 2.8 (2.7) in the RL-group. Based on these means (SD), we need $n=46$ patients per group with an α level of 5% (2-sided) and for a power of 90%.

Non-compliance and dropout rates are expected to be rather low with regard to the massive impact of impaired visual acuity on activities of daily and social living. Regarding the CoRaLa I patients one participant (of 22) was lost (after 15 months) and 2 per arm died after long-term observation of more than 4 years. Although (extended) oversampling is not needed with regard to the confirmatory analysis within the FAS and a time-to-event primary endpoint, a major interest of the trial focuses on mid-/long-term differences between the treatments, too. Therefore, we amply plan with 20% dropouts and intend to include at least 110 patients to learn as much as possible on the effect of the additional laser treatment on the further need of regular Ranibizumab injections in long-term and ensure sufficiently precise estimations after two year of observation.

9.5 Statistical Methods

9.5.1 Analysis Population

Full analysis set

The full analysis set (FAS, based on the intention-to-treat (ITT) strategy) is defined by all randomized patients with valid informed consent and (at least) a single study intervention performed.

Per protocol set

The per-protocol (PPS) set is defined by all patients belonging to the FAS without major violations of the study protocol.

The following protocol violations are classified as major:

- Violation of an eligibility criterion;

- Patients who did receive less than 75% of the intended treatment days without earlier success or other *relevant clinical reasons (including clinical reasons which require a postponed injection or a (timely) interruption of the series, death, (serious) adverse events) which may require a premature termination of the intervention*

This is not an exclusive list. In the light of protocol violations which actually may occur during study conduct, all major protocol violations will be defined, e.g. as part of the statistical analysis plan. The completed list will be finalised before database closure and start of the final analysis.

Safety analysis set

The safety population is defined by all randomized patients belonging to the FAS. In safety analyses, patients will be classified whether or not they received at least a single laser therapy, irrespective of the randomized group allocation.

In analyses of *secondary and complementary* endpoints all patients will be excluded in whom a new onset of RVO was found after a previous success since this would cause a bias.

The aspects of relapses and recurrence of ME after a reported success will be reported separately.

9.5.2 Planned Methods for Analysis

Analysis of the *primary endpoint* (within the FAS, [31]) will follow the intent-to treat principle and will be based on COX regression with the stratification factor baseline BCVA (≤ 55 letters vs > 55 letters) as fixed covariate for confirmatory analysis.

Further models will include potentially prognostic factors and compliance for sensitivity reasons. The assumption of proportional hazard may be justified although no similar data are available by now. It will be checked and otherwise adequately dealt with. Kaplan-Meier curves provide time without treatment success per arm.

The *number of Ranibizumab injections* required after the initial three injections will be analysed by an ANCOVA *model* including treatment as factor and baseline BCVA as covariate (also used for stratification); for sensitivity reasons, further models may include the same prognostic factors of potential relevance as selected for analyses of the primary endpoint.

To adequately analyse the long-term *courses of BCVA and CST* at the end of study we require that patients with early treatment success have further mandatory visits beyond success since - based on CoRaLa I data - we expect rather different event times with regard to the chosen primary endpoint. Given the 6 monthly visits to determine "success", we assume that this will lead to only few additional visits per patient

In each patient, BCVA and CST will be analysed at 6 time points: at baseline visit, and after 12, 16, 20, 24 and 29 months. Analyses of both secondary endpoints are identically structured: mean changes from baseline mean will be analysed using a repeated measurement linear mixed model without intercept containing the fixed, categorical effects of

- visit (as named),
- treatment (RL vs R-only),
- treatment by visit interaction,
- low BCVA pre-treatment value (yes / no) as well as
- a patient-specific, visit random effect.

An unstructured (co-)variance structure will be used to model the residual within-patient errors. If this analysis fails (does not converge), a compound symmetry structure corresponding to a constant correlation will be used. The analysis will be based on restricted maximum likelihood

(REML). The contrast of interest is the treatment by visit interaction at 29 months. Respective inference will be based on Wald type confidence intervals and respective p-values.

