5.3.2 Compliance

Study interventions will be administered on the study site; therefore, compliance with the dosing of study drug will be monitored by a review of clinical records.

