9.2 End Points

9.2.1 Primary End Point

Primary efficacy endpoint is the time to treatment success, defined as time from randomisation until the date of last criteria-based intravitreal injection in case that thereafter a treatment-free period for (at least) 6 months was observed.

Objective criteria for further treatment indication (according to details in section 6.3) have to be fulfilled for decisions regarding further re-treatment.

Drop-outs/deaths without earlier success will be censored at the end of their observation time and all other patients without documented success at month 24 or 29 after randomisation (in case of no treatment indication at the last regular visit to state or deny a late success).

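### Compliance arises after randomisation, so a Cox model adjusted for it is not a valid check on the primary ITT result

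*Protocol*

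**What the plan says.** Section 9.5.2 sets the confirmatory analysis of the primary endpoint, in the full analysis set under intention to treat, as "COX regression with the stratification factor baseline BCVA (≤ 55 letters vs > 55 letters) as fixed covariate for confirmatory analysis". That model contains no variable measured after randomisation. The next paragraph adds: "Further models will include potentially prognostic factors and compliance for sensitivity reasons". The Biometry row of the English synopsis repeats this.

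Other sections bear on what compliance is:

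- Section 5.3.2: "compliance with the dosing of study drug will be monitored by a review of clinical records". The information therefore accrues during treatment.
- Section 6.3: "The experimental group will receive an additional targeted laser photocoagulation of the peripheral areas of capillary non-perfusion". Control patients have no laser sessions to attend or miss.
- Section 9.5.1 has the nearest thing to a definition, a major violation for the per-protocol set: "Patients who did receive less than 75% of the intended treatment days without earlier success or other" relevant clinical reasons.
- Section 9.2.1 takes the event time from an injection date: "defined as time from randomisation until the date of last criteria-based intravitreal injection in case that thereafter a treatment-free period" of at least six months.
- Section 9.4 states: "Non-compliance and dropout rates are expected to be rather low". It gives no rate.

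The rest of the plan is more restrained. For the number of injections, section 9.5.2 would add only the prognostic factors chosen for the primary endpoint. The Biometry row of the German synopsis does not mention compliance.

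**The concern.** A sensitivity analysis should ask the primary question again under different assumptions. Adding a baseline covariate does that, because randomisation balances it in expectation. Adding compliance does not. Within a compliance class, RL and R-only patients need not be comparable: the classes are formed after allocation, under different treatment burdens, and possibly for reasons that also predict success. The adjusted hazard ratio then mixes any laser effect with that selection.

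If the adjusted and ITT results disagreed, a sound primary result could be doubted. If they agreed, an unsound one could be given unearned support. The protocol states that these models will include the term, so the choice is fixed here and is more than a detail left to the SAP.

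**Working it through.** **1. Does the point touch the planned sample size?** Section 9.4 gives the inputs: "setting a two-sided significance level α at 5%, and requiring 90% power", with 50% (R-only) and 20% (RL), read as patients still without success at two years.

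- HR for success = ln(0.2)/ln(0.5) = 2.32, and ln(2.32) = 0.842.
- Events (Schoenfeld) = 4 × (1.960 + 1.282)² / 0.842² = 59.2.
- Mean success proportion = (0.50 + 0.80)/2 = 0.65.
- N = 59.2/0.65 = 91.1, so 46 per arm and 92 in total.

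This reproduces the protocol's 92. No compliance term enters it, so the figure stands.

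**2. Is compliance a valid adjustment variable?**

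- *Timing:* it is recorded during treatment (5.3.2), hence after randomisation.
- *Arm:* only RL has laser sessions (6.3), sites perform them, and only the BCVA assessor is described as blinded (3.2.1, 6.3, 7).
- *Outcome:* prognosis can plausibly affect both adherence and success. If the 75% rule of 9.5.1 were used as the measure, the class would also depend on whether success had already occurred, since earlier success excuses a shortfall. That the rule is meant is an inference.

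**3. How far could the hazard ratio move?** The protocol supplies none of the needed inputs, so every value below is assumed.

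*Set-up A* (N = 110, 800 runs). Success times are exponential with baseline hazard ln(2)/24 per month. An unmeasured standard normal prognostic factor u has log-hazard coefficient 0.8. Follow-up is cut at 23 months. The logit of non-compliance is −1.8 in controls and −1.0 − s·u in RL, where s is the dependence on prognosis. This gives 1/(1 + e^1.8) = 14% in controls and, for s = 0, 1/(1 + e^1.0) = 27% in RL (30% and 35% for s = 1 and 2).

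| Truth | s | HR, ITT model | HR, compliance added | Rejection, ITT → adjusted |
|---|---|---|---|---|
| No effect | 0 | 1.01 | 1.01 | 5.1% → 6.1% |
| No effect | 1 | 1.01 | 1.08 | 5.1% → 5.5% |
| No effect | 2 | 1.01 | 1.16 | 5.1% → 8.3% |
| Planned effect | 0 | 2.00 | 2.01 | 79% → 80% |
| Planned effect | 1 | 2.00 | 2.18 | 79% → 87% |
| Planned effect | 2 | 2.00 | 2.40 | 79% → 92% |

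The Monte Carlo standard error of a 5% rejection rate is √(0.05 × 0.95/800) = 0.8 percentage points, so only the 8.3% stands clear of noise. The 79% is not the trial's power: the assumed unmeasured factor pulls the average HR from 2.32 to 2.00.

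*Set-up B* (600 runs). Missed treatments are Poisson with mean 0.05 per month on treatment. Under the planned effect the HR falls from 1.98 to 1.91 and rejection from 79% to 72%.

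*Set-up C* (100,000 per arm, no effect). Latent severity drives compliance and success, and RL raises compliance. The HR goes from 1.00 to 0.977 with moderate links and 0.934 with strong links. The numerical link strengths are not available, so this shows direction only.

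**4. Scale.** With 59.2 events the standard error of the log HR is about 2/√59.2 = 0.26. The largest shift in A under no effect is ln(1.163) − ln(1.010) = 0.141, or 0.54 standard errors. The larger shift in C is |ln(0.934)| = 0.068, or 0.26 standard errors. The planned effect is 0.842.

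**The case against.** Nothing confirmatory depends on these models. The sentence also covers baseline prognostic factors, which are legitimate, and it does not say that compliance enters every further model. Its definition and form of entry are normal SAP content. Non-compliance is expected to be low, and the simulated shifts are about half a standard error or less. All of this stands and keeps the point small. It does not rescue the compliance term: any on-treatment measure is post-randomisation, and entering it as time-dependent would remove use of future information but not the shared causes.

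A reader might go further and infer that a missed injection mechanically produces success, because section 9.2.1 speaks of a treatment-free period, and that this adds to the bias. The documents do not support that. Section 6.3 grants success only if OCT shows no macular edema over six months. Section 1.2.1, the flow chart notes and the German synopsis speak of no further need for injection. An indicated but missed injection means edema was present, which blocks success. A wholly missed visit, with no OCT, leaves at most a weak link.

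Nor would such a link clearly add to the bias. In a further null simulation (assumed inputs, 100,000 per arm), introducing a direct effect of non-compliance on success moved mainly the unadjusted HR, from 0.999 to 0.919 with moderate links. The adjusted HR barely moved, from 0.958 to 0.951. With strong links the adjusted HR was 0.880 to 0.893, so the values from set-ups A and C are not bounds.

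**Conclusion.** The concern holds in a limited form. A compliance-adjusted Cox model is not a valid check on the ITT result, because it conditions on a variable that arises after randomisation, can differ by arm and can share causes with success. Agreement or disagreement with the primary model would reflect why patients fail to comply more than how robust the ITT result is.

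Neither the direction nor the size of the distortion follows from the protocol. Under no effect the adjusted HR went to 0.93 or to 1.16 according to whether RL was assumed to raise or lower compliance and how strongly prognosis was involved. The distortion is close to nil if non-compliance is rare or unrelated to prognosis. It would be wrong to infer a known bias, a threat to the confirmatory test, or that all the further models are invalid. The primary ITT Cox model, the 5% level and the planned sample size are untouched, and models with baseline factors only remain sound. Severity is minor.

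**What to change.** In section 9.5.2 and in the Biometry row of the English synopsis, delete compliance from the covariates of the further models and state that these models use baseline covariates only. The German synopsis needs no change on this point.

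Examine adherence only in the per-protocol set already defined in section 9.5.1. Label that analysis supportive, because membership of the set is also determined after randomisation and the same selection can operate there.

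The cost is a text amendment and the loss of one exploratory model. No new data are needed, and the sample size and confirmatory analysis do not change.
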